5.3. Baseline Definitions

5.3.1. Part A single dose (cross-over)

- Baseline definitions are applied to each period.
 - The baseline value will be the latest pre-dose assessment with a nonmissing value, including those from unscheduled visits unless otherwise stated below: For ECGs and Vitals, baseline is defined as the mean of triplicate measurement at the latest pre-dose assessment.
 - For PD S4 assay, MCP-1, IL-6 and TNF, baseline is defined as an average of the day -1 1pm and day 1 pre-dose samples.
- If time is not collected, Day 1 assessments are assumed to be taken prior to first dose and used as baseline.
- Replicate assessments at a timepoint will be averaged, and the mean value will be used.
- Unless otherwise stated, if baseline data is missing no derivation will be performed and baseline will be set to missing.

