12-Lead ECGs	x	x	x					x	x		x	x	x	x	See separate Period 4 Schedule of Activities	x		12 Lead ECGs will be performed in triplicate at screening, Day-1, Day 1 pre- dose, Day 2 and Day 3. Single ECGs will be performed at other time points and if any cardiac symptoms are experienced. ECGs to be performed prior to blood draws and dosing where these fall at the same nominal time.
Telemetry			<==										===>		dule			from 1 h pre-dose to 24 h post-dose
Holter monitoring (24 hours)	Х														of Activ			If a participant is rescreened the Holter will not need to be repeated.
HIV, Hep B, Hep C	Х														ities			
Haematology	х	х									х		x	x		x		Fasted screening samples. 24 and 48 hour samples will be taken prior to participants receiving breakfast
Coagulation	х										х		x	x		х		Fasted screening samples. 24 and 48 hour samples will be taken prior to participants receiving breakfast

CONFIDENTIAL

Procedure	Screening (up to 35 Days prior to Day 1)					-	Treatm Da	ient Pe ay 1	eriod 1	-3			Day 2	Day 3	Treatment Period 4	Follow-up 1 (7-14 days post-last dose)	Follow-up 2 (5 we dose ± 3 c	Notes
	Days prior to	Day -1	Pre-dose	0 h	15 mins	30 mins	1 h	2 h	4 h	6 h	4 8	12 h	24 h	48 h	eriod 4	lays post-last	5 weeks after last ⊦ 3 days)	The 2nd follow up visit is only required for those participants where challenges are being administered and blisters induced i.e. treatment period 4
Clinical Chemistry	х	х									х		x	Х		х		Fasted screening samples. 24 and 48 hour samples will be taken prior to participants
Urinalysis	х	х									х		x	х		х		Fasted screening samples. 24 and 48 hour samples will be taken prior to participants receiving breakfast
Drug / Alcohol Test	Х	Х																
Urine Cotinine	Х	Х																
Visual forearm check (cosmetic assessment or blister healing where appropriate)	X	Х														X	X	 Visual forearm checks are only required if participant is scheduled to take part in treatment period 4. Details of checks: Screening check prior to first treatment period (cosmetic assessment) Day -1 check in treatment Period 3 only. Between Day -1 and Day 2 (ie 48 hour window) (cosmetic assessment) Period 4 (cosmetic assessment) Period 4 (cosmetic assessment and blister healing). For further detail on time points in Period 4 see Section 2.1.1. Follow-up visits 1 and 2 (blister healing)

CONFIDENTIAL

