Haematology	x	х	x	x		x			•	x				х	х	x	x	x	x	Fasted screening samples. Sample to be taken pre-dose on Day 1, 2, 4, 8, 12 and 13. See Section 2.3.1 for haematology time points on Day 14, 15 and 16. Follow-up visit samples do not require fasting.
Coagulation	х	x				x				x						х			x	Fasted screening samples. Sample to be taken pre-dose on Day - 1, 4 and 8. See Section 2.3.1 for further details of Day 14 sample timings. Follow-up visit samples do not require fasting
Fasting lipids and glucose	х	x				x				x						х				Fasted screening samples. Sample to be taken pre-dose on each day. Both fasting lipids and glucose will be tested from same sample. Follow-up visit samples do not require fasting
Clinical Chemistry	х	х	х	х		х				х				х	х		х	Х	х	Fasted screening samples. Sample to be taken pre-dose on each day. Follow-up visit samples do not require fasting. GGT and CK to be included at screening, Day-1 and follow up only
Urinalysis	Х	Х	Х	Х		Х				Х				Х				Х	Х	Fasted screening samples. Sample to be taken pre-dose on each day. Follow-up visit samples do not require fasting
Drug / Alcohol Test	Х	Х																		Ad-hoc testing to be performed in the event of any cardiac arrhythmias, as close as possible to the time of occurrence
Urine Cotinine	Х	Х																		
AE / SAE review	3	SAEs										form se ur						visit; A it.	\Es	
Concomitant Medication Review			Мо	nitor	ed co	ontinu	uousl	y fror	n firs	t dos	e unt	il the	end	of th	e trea	atme	nt pe	riod		
Treatment / agent administration	on																			
Study Drug Administration			Х	Х	Х	Х	Х	Х	Х	Х	Х	Х	Х	Х	Х	Х				Once-daily in the morning on Days 1-14 inclusive.
Pharmacokinetics, Pharmacody	/namic	s an	d Ge	netic	s Sa	mple	e													

Durantum	Screening (up to 35 prior to Day 1)	Follow-up 1 (7-14 days post-last dose) Treatment Period Day 16 Day 16 Day 16 Day 12 Day 16 Day 12 Day 17 Day 16 Day 10 Day 10 Day 1 Day 10 Day 2 Day 1											Notes							
Procedure	up to 35 Days Day 1)	Day -1	Day 1	Day 2	Day 3	Day 4	Day 5	Day 6	Day 7	Day 8	Day 9	Day 10	Day 11	Day 12	Day 13	Day 14	Day 15	Day 16	l (7-14 days st dose)	
Blood sampling for systemic PK [S1] and [S2]			x	х		x				x				x		x	x	x		On Day 1 samples will be taken at pre-dose, 15mins, 30mins, 1h, 2h, 4h, 6h, 8h, 12h and 24h post-dose, Pre-dose samples Days 4, 8 and 12. See Section 2.3.1 for Day 14, 15 and 16 sample timings. Ad-hoc sample to be taken in the event of any cardiac arrhythmias, as close as possible to the time of occurrence

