9.4.7. Clinical Safety Laboratory Assessments

- Refer to Appendix 2 for the list of clinical laboratory tests to be performed and to the SoA for the timing and frequency.
- The investigator must review the laboratory report, document this review, and record any clinically relevant changes occurring during the study in the AE section of the CRF. The laboratory reports must be filed with the source documents.
- All laboratory tests with values considered clinically significantly abnormal during participation in the study or within 7-14 days after the last dose of study treatment should be repeated until the values return to normal or baseline or are no longer considered significantly abnormal by the investigator or medical monitor.
- If such values do not return to normal/baseline within a period of time judged reasonable by the investigator, the etiology should be identified and the sponsor notified.
- All protocol-required laboratory assessments, as defined in Appendix 2, must be conducted in accordance with the laboratory manual and the SoA.
- If a cardiac arrhythmia occurs, a PK sample and drugs of abuse test should be taken as close to the time of the event as possible.
- Laboratory results at Day -1 are for the purposes of providing baseline values prior to dosing. The review of laboratory abnormalities at Day -1 for eligibility will be based on Investigator discretion and clinical judgement.

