13.4. Appendix 4: Data Display Standards & Handling **Conventions**

13.4.1. **Reporting Process**

Software

Software				
• The currently supported versions of SAS software will be used.				
Reporting Area				
HARP Server	: UK1SALX00175			
HARP	: \arprod\gsk3358699\mid207546\data_look_01			
Compound	: \arprod\gsk3358699\mid207546\final_01			
Analysis Datasets				
• Analysis datasets will be created according to Integrated Data Standards Library				

Analysis datasets will be created according to Integrated Data Standards Library (IDSL) Legacy GSK A&R dataset standards.

Generation of RTF Files

RTF files will be generated for all tables within the final 01 reporting effort for SAC. •

13.4.2. **Reporting Standards**

General

The current GSK Integrated Data Standards Library (IDSL) will be applied for • reporting, unless otherwise stated (https://spope.gsk.com/sites/IDSLLibrary/SitePages/Home.aspx): 4.03 to 4.23: General Principles 5.01 to 5.08: Principles Related to Data Listings • 6.01 to 6.11: Principles Related to Summary Tables • 7.01 to 7.13: Principles Related to Graphics • Do not include participant level listings in the main body of the GSK Clinical Study Report. All participant level listings should be located in the modular appendices as ICH or non-ICH listings All data displays (Tables, Figures and Listings) will use the term "Subject" which • reflects CDISC and GSK data display standards terminology. Formats • GSK IDSL Statistical Principles (5.03 & 6.06.3) for decimal places (DPs) will be adopted for reporting of data based on the raw data collected, unless otherwise stated. Numeric data will be reported at the precision collected on the eCRF. • • The reported precision from non eCRF sources will follow the IDSL statistical

principles but may be adjusted to a clinically interpretable number of DP's. Planned and Actual Time

- Reporting for tables, figures and formal statistical analyses: •
 - Planned time relative to dosing will be used in figures, summaries, statistical • analyses and calculation of any derived parameters, unless otherwise stated.

207546

- The impact of any major deviation from the planned assessment times and/or scheduled visit days on the analyses and interpretation of the results will be assessed as appropriate.
- Reporting for Data Listings:
 - Planned and actual time relative to study drug dosing will be shown in listings (Refer to IDSL Statistical Principle 5.05.1).

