13.9.5. Safety Tables

Part A

Safet	Safety: Tables					
No.	Population	IDSL / Example Shell	Title	Programming Notes	Deliverable [Priority]	
Adve	rse Events (Al	Es)			•	
2.1.	Safety	AE5a	Part A: Summary of All Adverse Events by Maximum Intensity by System Organ Class and Preferred Term	Add footnote listing the subjects who re-enrolled in other Parts (only add this footnote if they had AEs both here and in another Part) Include total column.	SAC	
2.2.	Safety	AE5a	Part A: Summary of All Drug Related Adverse Events by Maximum Intensity by System Organ Class and Preferred Term	Include total column.	SAC	
2.3.	Safety	AE16	Part A: Summary of Serious Adverse Events by System Organ Class and Preferred Term (Number of Subjects and Occurrences)	For studies with few events/participants listing is sufficient: discuss this option with your disclosure representative.	SAC	
2.4.	Safety	AE15	Part A: Summary of Common (>=5%) Non-serious Adverse Events by System Organ Class and Preferred Term (Number of Subjects and Occurrences)		SAC	
2.5.	Safety	AE3	Part A: Summary of Common (>=5%) Adverse Events by Overall Frequency		SAC	

Safety	Safety: Tables						
No.	Population	IDSL / Example Shell	Title	Programming Notes	Deliverable [Priority]		
2.6.	Safety	AE3	Part A: Summary of Adverse Events Leading to Permanent Discontinuation of Study Treatment or Withdrawal from Study		SAC		
2.7.	Safety	AE3	Part A: Summary of Non-Serious Drug-Related Adverse Events by Overall Frequency		SAC		
2.8.	Safety	AE3	Part A: Summary of Serious Drug-Related Adverse Events by Overall Frequency		SAC		
Labor	atory						
2.9.	Safety	LB1	Part A: Summary of Chemistry Changes from Baseline	Order parameters alphabetically.	SAC		
2.10.	Safety	LB17	Part A: Summary of Worst Case Chemistry Results by PCI Criteria Post-Baseline Relative to Baseline	Order parameters alphabetically, include parameters with PCI criteria listed in Appendix 7.	SAC		
2.11.	Safety	LB15	Part A: Summary of Worst Case Chemistry Results Relative to Normal Range Post-Baseline Relative to Baseline	Order parameters alphabetically, include parameters with Normal Ranges listed in Appendix 7.	SAC		
2.12.	Safety	LB1	Part A: Summary of Hematology Changes from Baseline	Order parameters alphabetically.	SAC		

Safety	Safety: Tables						
No.	Population	IDSL / Example Shell	Title	Programming Notes	Deliverable [Priority]		

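### The Part A fallback in SAP 5.3.1 would turn an untimed 6 h or 8 h safety-laboratory sample into the period's pre-dose baseline

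*SAP*

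**What the plan says.** SAP 5.3.1 sets the Part A baseline in three steps that matter here.

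- Scope: "Baseline definitions are applied to each period".
- Default: "The baseline value will be the latest pre-dose assessment with a nonmissing value", with unscheduled visits included.
- Fallback: "If time is not collected, Day 1 assessments are assumed to be taken prior to first dose and used as baseline".

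ECGs, vital signs and the ex vivo cytokine assay have their own baseline definitions in the same section. The safety laboratory tests do not, so they follow the default and the fallback.

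Protocol 9.4.7 names the laboratory baseline: "Laboratory results at Day -1 are for the purposes of providing baseline values prior to dosing".

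SAP 13.4.2 adds a general reporting convention: "Planned time relative to dosing will be used in figures, summaries, statistical" analyses and derived parameters, except where something else is stated. SAP 13.3.1 lists laboratory data among the planned events that carry a time slice.

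**The concern.** SAP 5.3.2 repeats the fallback for Part C, where it does no harm to laboratory data. The protocol 2.3 note for haematology reads "Sample to be taken pre-dose on Day 1, 2, 4, 8, 12 and 13", and chemistry and urinalysis are also pre-dose on dosing days. Part A is scheduled differently: the pre-dose column on Day 1 is empty for all four safety laboratory tests. A rule that presumes an untimed Day 1 sample is pre-dose is therefore wrong for every scheduled Part A sample of this kind.

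What is at stake is the laboratory part of the primary safety objective. Table 2.9 ("Part A: Summary of Chemistry Changes from Baseline"), its haematology counterpart (2.12) and the worst-case tables (2.10, 2.11, 2.13, 2.14) are all relative to baseline. If a post-dose value becomes the baseline, an early drug effect vanishes from the record, and its recovery can read as a change in the opposite direction. In Period 4 the mislabelled sample would also follow the in vivo challenge, after which protocol 8.1.3 expects transient haematology changes.

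**Working it through.** **Step 1: what is scheduled.** Source: the rows of protocol 2.1 and 2.1.1, reproduced in SAP 13.1.1 and 13.1.1.1. The protocol 2.1 note "24 and 48 hour samples will be taken prior to participants receiving breakfast" covers the two later time points.

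| Test | Periods 1-3 | Period 4 |
|---|---|---|
| Haematology, chemistry, urinalysis | Screening, Day -1, **8 h**, 24 h, 48 h, follow-up 1 | Day -1, **6 h**, 24 h, 48 h |
| Coagulation | Screening, **8 h**, 24 h, 48 h, follow-up 1 | **6 h**, 24 h, 48 h |

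The bold entry is the only Day 1 sample in each cell. None is pre-dose. Coagulation has no Day -1 sample either, so within a period no scheduled value competes with the mislabelled one.

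**Step 2: effect on one record.** Let the true value be B on Day -1, B + e at 8 h, B + f·e at 24 h and B + g·e at 48 h.

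- Day -1 as baseline: changes are e, f·e, g·e.
- 8 h value as baseline: changes are 0, (f - 1)·e, (g - 1)·e.

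The 8 h effect is removed exactly, and each later change is shifted by -e. The values of f and g are not in the documents, so a range is shown:

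| f, g (assumed) | True changes | Changes under the fallback |
|---|---|---|
| 1, 1 | e, e, e | 0, 0, 0 |
| 0.5, 0.25 | e, 0.5e, 0.25e | 0, -0.5e, -0.75e |
| 0, 0 | e, 0, 0 | 0, -e, -e |

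Invented neutrophil values show the sign change. Take 4.0 on Day -1, 2.8 at 8 h and 3.8 at 24 h. The correct changes are 2.8 - 4.0 = -1.2 and 3.8 - 4.0 = -0.2. Under the fallback they are 0 and 3.8 - 2.8 = +1.0.

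**Step 3: weight of one record.** Protocol 10.2.1 gives six active participants per dose level in Part A, so one record is 1/6 = 17% of a dose group in Periods 1-3. In Period 4 both cohorts receive the same dose, with six active each (protocol 5.1.1.2). SAP 5.2 displays them under one label, so the share is 1/12 = 8%. With e = -1.2 in the affected participant, the group mean 24 h change moves by 1.2/6 = 0.2 or 1.2/12 = 0.1.

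**Step 4: Period 4 timing.** Protocol 2.1.1 anticipates the challenge 0.5 to 2 h after dosing. The 6 h sample then falls 6 - 2 = 4 h to 6 - 0.5 = 5.5 h after LPS or the start of the GM-CSF infusion.

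**The case against.** The strongest reply is that the rule may never act. It needs a missing time, and nothing in either document says that any Part A laboratory time is missing. Laboratory results are loaded electronically, and for a timed record the default rule already returns Day -1 for haematology, chemistry and urinalysis. This stands: the number of affected records is unknown and may be zero.

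The second reply is that nominal time already governs. Laboratory data carry time slices, summaries use nominal visits (SAP 13.2.1), and a record labelled 8 h is post-dose by its label. This stands only in part. The planned-time convention yields wherever something else is stated. SAP 5.3.1 does state something else, and no text says which prevails. A programmer who follows 5.3.1 literally would assign the wrong baseline.

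Third, the consequences are bounded. The analysis is descriptive, and Listings 18 and 19 still show values outside the normal range or of potential clinical importance, mostly against absolute limits. Urinalysis is outside Tables 2.9 to 2.14. All of this stands.

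A reader might go further and infer that the rule spoils ECG and vital-sign baselines as well. The documents do not support that. SAP 5.3.1 bases those baselines on the triplicate mean at the latest pre-dose assessment. Part A ECGs are triplicate pre-dose and single at the later Day 1 times. Blood pressure and pulse are also single post-dose, except around Cmax and after LPS. Nor does the point reach every Day 1 sample: PK, ex vivo cytokine, circulating-protein, gene-panel and metabolite urine samples all have pre-dose collections in Periods 1-3.

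**Conclusion.** The point holds for Part A safety laboratory tests. SAP 5.3.1 contains a rule that gives a wrong baseline whenever it acts on one of their scheduled Day 1 samples, and it conflicts with protocol 9.4.7. For an affected record, the 6 h or 8 h change is lost in full and the 24 h and 48 h changes are shifted by that same amount. The weight is 1 of 6 active participants per dose in Periods 1-3 and about 1 of 12 in Period 4.

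The conclusion rests on the schedule as printed and on a literal reading of the fallback. The size of e and its persistence are assumptions.

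A reader might infer that the Part A laboratory tables are in fact wrong, or that the drug effect is cancelled throughout. Neither follows. No untimed record is documented, and cancellation is exact only at the 6 h or 8 h point. At 24 h and 48 h it would need an effect that persists unchanged. This is a conditional error in a stated rule, with coagulation the most exposed test.

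**What to change.** In SAP 5.3.1, replace the fallback with wording to this effect: *If clock time is missing, the record is classified by its planned (nominal) time point; a record with a post-dose nominal time point is never used as baseline. The latest pre-dose value, including unscheduled pre-dose values, remains the baseline (Day -1 for Part A haematology, chemistry and urinalysis).* An unscheduled Day 1 record with neither a clock time nor a planned time point cannot be classed and should not serve as baseline.

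Add one sentence for Part A coagulation: its baseline is the screening value, or it is set to missing. A rule that admits only Day -1 or Day 1 pre-dose records would leave clotting parameters with no scheduled baseline in any Part A period. If screening is chosen, its age should be acknowledged: with at least 28 days between a cohort's periods, it precedes Period 3 dosing by more than 2 × 28 = 56 days for anyone enrolled from Period 1.

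Leave the Part C sentence unchanged for laboratory data.

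The cost is a few lines of SAP text and a check of the baseline derivation; the planned time points are already in the data. The sponsor should also count the untimed Part A Day 1 safety-laboratory records. If the count is zero, no result changes.

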5.3.2. Part C repeat dose (parallel)

- The baseline value will be the latest assessment prior to any dosing with a non-missing value, including those from unscheduled visits unless otherwise stated below:
 - For ECGs and Vitals, baseline is defined as the mean of triplicate measurement at the latest pre-dose assessment.
- For PD S4 assay, MCP-1, IL-6 and TNF, baseline is defined as an average of the Day -1 1pm and Day 1 pre-dose samples. If time is not collected, Day 1 assessments are assumed to be taken prior to first dose and used as baseline.
 - Replicate assessments at a timepoint will be averaged, and the mean value will be used.
- Unless otherwise stated, if baseline data is missing no derivation will be performed and baseline will be set to missing.

5.4. Re-enrolled Participants

The protocol allows participants to take part in more than one cohort in this study. Instances where this occurred were as follows:

Subject Number				
Cohort 1	Cohort 2	Cohort 2 Cohort 4 Cohort 5		
PPD		PPD		
	PPD		PPD	
		PPD	PPD	

207546

Participants who take part in more than one cohort are to be considered distinct participants for the purposes of the reporting of all the data in this study. However relevant displays will be footnoted.

5.5. Other Considerations for Data Analyses and Data Handling Conventions

Other considerations for data analyses and data handling conventions are outlined in the appendices.

Section	Component
13.2	Appendix 2: Assessment Windows
13.3	Appendix 3: Study Phases and Treatment Emergent Adverse Events
13.4	Appendix 4: Data Display Standards & Handling Conventions
13.5	Appendix 5: Derived and Transformed Data
13.6	Appendix 6: Reporting Standards for Missing Data
13.7	Appendix 7: Values of Potential Clinical Importance and Normal Ranges

6. STUDY POPULATION ANALYSES

The study population analyses will be based on the Safety population, unless otherwise specified.

Study population analyses including analyses of participant's disposition, protocol deviations, demographic characteristics, prior and concomitant medications, and exposure will be based on GSK Core Data Standards.

Details of the planned displays are presented in Appendix 9: List of Data Displays.

7. EFFICACY ANALYSES

There are no efficacy analyses to be included in this FTIH study.

8. SAFETY ANALYSES

The safety analyses will be based on the Safety population, unless otherwise specified.

8.1. Adverse Events Analyses

The definition of an AE is detailed in Appendix 4 of the protocol.

Analyses of AEs will include all events, classified as in Section 13.3.

Adverse events analyses including the analysis of adverse events (AEs), Serious (SAEs) and other significant AEs will be based on GSK Core Data Standards.

Details of the planned displays are presented in Appendix 9: List of Data Displays.

207546

8.2. Clinical Laboratory Analyses

Laboratory evaluations will be based on GSK Core Data Standards and will include:

- Hematology laboratory tests
- Chemistry laboratory tests
- Urinalysis
- Liver function tests
- Other screening tests

Clinical laboratory analyses will include all assessments post-baseline. Unscheduled visits will not be included in summary tables and figures, but will be included in listings – see Section 13.4.2.

Details of the planned displays are presented in Appendix 9: List of Data Displays.

The laboratory assessments for each category are displayed below (Table 6 of the protocol):

Laboratory Assessments		Para	meters			
Haematology						
Clotting parameters: APTT PT times Fibrinogen	Platelet Count RBC Count Haemoglobin Haematocrit	RBC Indices: MCV MCH %Reticulocyte	MCV		WBC count with Differential: Neutrophils Lymphocytes Monocytes Eosinophils Basophils	
Clinical Chemis	strv ¹				1	
CRP	Blood Urea Nitrogen (BUN)	Potassium	Aspartate Aminotransfer (AST)/ Serum Glutamic- Oxaloacetic Transaminase (SGOT)		Total and direct bilirubin	
Albumin	Creatinine	Sodium	Alanine Aminotransfer (ALT)/ Serun Glutamic-Pyru Transaminase (SGPT)	1	Total Protein	
Glucose (fasting during Part C ²)	Calcium	Alkaline phosphatase	Cholesterol ^{2,3}		Low Density Lipoprotein ^{2,3}	
High Density Lipoprotein ^{2,3}	Triglycerides ^{2,3}	Gamma- glutamyl	Creatine kinas (CK) ⁴	e		

207546

Laboratory Assessments	Parameters		
	transferase (GGT) ⁴		
Routine Urinaly	vsis		
• Microscopic e	xamination (if blood or protein is a	bnormal)	

- 1. NOTES:
- Details of liver chemistry stopping criteria and required actions and follow-up assessments after liver stopping or monitoring event are given in Section 8.1 and Appendix 7 of the protocol. All events of ALT ≥3 × upper limit of normal (ULN) and bilirubin ≥2 × ULN (>35% direct bilirubin) or ALT ≥3 × ULN and international normalized ratio (INR) >1.5, if INR measured, which may indicate severe liver injury (possible Hy's Law), must be reported as an SAE (excluding studies of hepatic impairment or cirrhosis).
- 2. In Part C at certain time points as per the SoA lipids and glucose samples are required to be taken fasted.
- 3. Screening samples are required to be taken fasted.
- 4. To be analysed at screening, Day-1 and follow up only 1.

